### 2.2 Primary Objective:

#### 2.2.1 Treatment effectiveness (Aim 1)

To compare the proportions of participants in the Enhanced Usual Care (EUC) and Virtual Tobacco Treatment (VIT) study arms with biochemically-verified 7-day point-prevalence abstinence from cigarettes at 6-months post enrollment.

We will define biochemically-verified 7-day point-prevalence abstinence at 6 month follow-up by:

- saliva cotinine (< 15 ng/ml), or
- expired air CO (< 10ppm)

### 2.3 Secondary Objectives:

#### 2.3.1 Secondary treatment effectiveness (Aim 1)

Secondary smoking outcomes (5) include:

- Biochemically-verified 7-day point prevalence abstinence at 3-months follow-up
- Self-reported 7-day point prevalence cigarette abstinence at 3- and 6-months follow-up

- Significant reduction (> 50% reduction in reported number of cigarettes per day) in daily smoking from baseline to 3- and baseline to 6-months follow-up
- Continuous (no self-reported smoking since last survey point) and sustained abstinence at 6 months (cotinine-verified at 3-months and 6-months)

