### 2.1 Study Aims:

- 2.1.1 **Aim 1:** To assess treatment effectiveness, by comparing the proportions of participants in the Enhanced Usual Care (EUC) and Virtual Tobacco Treatment (VIT) study arms abstinent post enrollment.
- 2.1.2 **Aim 2:** To assess the potential effect of potential moderators (e.g., sociodemographics, medical and smoking history, cancer variables) on treatment effectiveness between the two arms.
- 2.1.3 **Aim 3:** To assess the processes of implementation and dissemination (acceptability, adoption, appropriateness, treatment fidelity, cost effectiveness, penetration/reach, and sustainability) of delivering tobacco treatment interventions at community oncology sites.

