### 6.2 Patient assessments

#### 6.2.1 Secondary smoking outcomes are commonly used in tobacco cessation trials and in our previous work. Reduction in smoking is important as most adult smokers reduce smoking as they try to quit; self-reported smoking status will additionally be used as it has been reported that deception of smoking status classification among cancer patients is low.

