##### 6.2.1.1 Self-reported quit status

Patients will be asked on the 3- and 6-month follow-up surveys, how long it has been since they last smoked a cigarette, even one or two puffs. "Current smoker" will be defined as smoking a cigarette, even one or two puffs, in the past 7 days. (See Supplemental Appendices B: 3-

month Survey and C: 6-month Survey). This will be used to generate secondary outcomes of self-reported 7-day point prevalence abstinence, continuous and sustained abstinence (See Section [2.3](#) for definitions).

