**6.2.1.2 Significant reduction in daily smoking**

Patients will be asked at baseline, 3-, and 6-month follow-ups, in the past 30 days, (1) on how many days they smoked cigarettes, and (2) how many cigarettes per day they typically smoked. “Significant reduction” will be defined as a > 50% reduction in cigarettes per day from baseline to 3- and 6-month follow-ups. (See Supplemental Appendix A: Baseline Survey)

**6.2.2 Exploratory objectives – Moderators and Mediators:** We will collect information on the following baseline factors and modifiable characteristics that may affect the association between treatment group and effectiveness outcomes. The following factors have been selected from the theoretical models, the Self-Regulation Model (SRM) and the Health Belief Model (HBM), that have informed this intervention, as well as based on our previous research.

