9.7 Plans for analyzing the secondary objectives: secondary treatment effectiveness (Aim 1)

The 5 secondary objectives (defined in Section 2.3) include various ways of measuring abstinence at different times of assessment. In order to adjust for multiple comparisons, differences will be considered significant at  $0.01/N=0.01/5=0.002$  level.

Similar to the primary objective is to compare the proportions of participants in the study arms with 7-day point-prevalence abstinence from cigarettes at 3-months post enrollment. We will define 7-day point-prevalence by saliva cotinine (< 15 ng/ml) or expired air CO (< 10 ppm). All participants who report being quit and no NRT or e-cigarette use will be requested to provide saliva samples, expired air CO will be measured in participants who report being quit and report concurrent NRT or e-cigarette use. If a participant is lost to follow-up or does not provide a saliva or CO sample, they will be considered a current smoker. Chi-square tests will be used to compare the outcomes between treatment groups.

Another secondary objective is to compare the proportions of participants in the study arms that self-report cigarette abstinence at 3-months. The participant will be asked, "In the past 7 days, have you smoked a cigarette, even a puff." With the answer recorded as "Yes" or "No". If the self-report response is unavailable, the participant will be considered a current smoker. Chi-square tests will be used to compare the outcomes between treatment groups. The process will be repeated using self-reported cigarette abstinence at 6-months.

Another secondary objective is to compare the proportions of participants in the study arms that report a continuous abstinence at 6 months. The participants will be asked, "How long has it been since you last smoked a cigarette (even one or two puffs)?" at 6 months. If the response is more than or equal to 3 months (e.g. time since previous survey), the participant will be considered having a continuous abstinence at 6 months. If the self-report response is unavailable, the participant will be considered not having a continuous abstinence at 6 months. Chi-square tests will be used to compare the outcomes between treatment groups.

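### The five secondary outcomes that Section 9.7 corrects for are not the list in Section 2.3: reduction of more than 50% in smoking is declared and defined but has no test, no place in the alpha family and no missing-data rule

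*Combined protocol and SAP*

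**What the plan says.** All places are in the combined protocol and SAP.

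- **Section 2.3.1** introduces the list with "Secondary smoking outcomes (5) include". One of its four bullets is a reduction of more than 50% "in daily smoking from baseline to 3- and baseline to 6-months follow-up".
- **Section 6.2.1** treats reduction as one of the secondary smoking outcomes and gives a reason: "Reduction in smoking is important as most adult smokers reduce smoking as they try to quit". Section 6.2.1.2 defines it from a 30-day recall that includes "how many cigarettes per day they typically smoked", asked at baseline, 3 and 6 months.
- **Section 9.7** states: "The 5 secondary objectives (defined in Section 2.3) include various ways of measuring abstinence at different times of assessment". It continues: "In order to adjust for multiple comparisons, differences will be considered significant at" 0.01/5 = 0.002. It then describes chi-square tests for five outcomes, none of them reduction.
- **Sections 9.2.2 to 9.2.6** number the same five outcomes 1 to 5 and give each a detectable difference at 0.002.
- **Section 9.8.1** lists six outcomes for the moderator work: those five and the primary.
- **Section 2.1**, Aim 1, compares proportions of the "study arms abstinent post enrollment" and does not mention reduction.
- **Section 9.5** classes participants lost to follow-up, or without a sample, as current smokers. Under 6.2.1.1, current smoker "will be defined as smoking a cigarette, even one or two puffs, in the past 7 days".

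**The concern.** Section 9.7 borrows its divisor from 2.3, but the two sections do not describe the same set. Reduction is declared in 2.3, justified in 6.2.1, defined in 6.2.1.2 and collected at all three time points. It then drops out of the analysis plan. Nobody reading the plan can tell whether it is to be tested, at what threshold, or how a participant without follow-up data is scored.

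What is at stake is how this one outcome is reported. A favourable reduction result could be presented with a p-value and no agreed threshold, or an unfavourable one could be left out, and the plan would not settle either case. Error control for the named tests is not at stake.

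**Working it through.** **1. Count the comparisons in 2.3 and compare with 9.7.**

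| Outcome | Comparisons in 2.3 | Tested in 9.7 | Powered in 9.2 |
|---|---|---|---|
| Verified abstinence, 3 months | 1 | yes | 9.2.2 |
| Self-reported abstinence, 3 and 6 months | 2 | yes, both | 9.2.4, 9.2.3 |
| Reduction of more than 50%, 3 and 6 months | 2 | no | none |
| Continuous abstinence, 6 months | 1 | yes | 9.2.5 |
| Sustained abstinence, 6 months | 1 | yes | 9.2.6 |
| **Total** | **7** | **5** | **5** |

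Counted by type, without time points, 2.3 has five rows, which may be what its figure means. That is a different five from 9.7: self-report counts once and reduction is included.

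**2. Reproduce the threshold.** 0.01/5 = 0.002, as stated. Five tests: 5 x 0.002 = 0.010. If reduction at both times were also tested at 0.002: 7 x 0.002 = 0.014. Dividing by seven gives 0.01/7 = 0.00143.

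**3. Likely size of any inflation.** The outcomes overlap, so the Bonferroni bound is loose. I modelled 3- and 6-month status as a bivariate normal cut at the plan's control rates (20, 31, 28, 20 and 13%). Sustained abstinence was nested within verified abstinence at 3 months and within self-reported abstinence, and abstainers were counted as reduced. Assumptions not in the documents: correlation between the two times 0.7 to 0.9, reduction rate 40 to 60%. Seven tests at 0.002 then have a family-wise error of about 0.010 to 0.011; five have about 0.0075.

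**4. Cost of counting seven.** The plan's method is the unpooled z-test: power = Φ(|p1 − p2| / SE − z), with SE = √{[p1(1 − p1) + p2(1 − p2)]/n} and z the two-sided critical value. Check against the table in 9.2.1: n = 140, 0.32 against 0.15, alpha 0.01 gives SE = 0.04965, 0.17/0.04965 − 2.576 = 0.848 and power 0.8018 (table: 0.80184). Detectable differences in points at 80% power and 140 per arm:

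| Section (control rate) | Printed | At 0.002 | At 0.00143 |
|---|---|---|---|
| 9.2.2 (20%) | 18 | 21.1 | 21.6 |
| 9.2.3 (31%) | 22 | 22.6 | 23.2 |
| 9.2.4 (28%) | 22 | 22.3 | 22.9 |
| 9.2.5 (20%) | 21 | 21.1 | 21.6 |
| 9.2.6 (13%) | 19 | 19.1 | 19.7 |

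Counting seven costs about 0.5 point.

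**5. The 9.2.2 figure.** With 0.38 against 0.20, SE = √(0.3956/140) = 0.05316. At alpha 0.002, 0.18/0.05316 − 3.090 = 0.296 and power is 0.616. At alpha 0.01 the detectable difference is 18.2 points, so the printed 18% matches the uncorrected level. Section 9.2.5 has the same inputs and prints 21%.

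**6. Missing reduction status.** A participant classed as a current smoker may or may not have cut down by more than half, and the two measures use different windows (7 and 30 days). At the prior trial's 86% survey response (Section 1.2.1), 0.14 x 154 = 21.6, so about 22 per arm would have no status. With 50% reduced among responders (assumed), the arm reads 0.86 x 0.50 = 43% if missing is not reduced, 50% on complete cases, and 43 + 14 = 57% if missing is reduced.

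**The case against.** A reader might infer that the plan tests seven outcomes with a divisor meant for five, and so under-corrects. The documents do not support that. No section plans seven tests. Sections 9.2, 9.7 and 9.8.1 agree on the same abstinence outcomes, 9.7 describes its set as ways of measuring abstinence, and Aim 1 concerns abstinence only. The divisor of five fits the tests that are named. Even if reduction were added at 0.002, the modelled error stays near 0.010, and that model rests on a correlation and a reduction rate that the plan does not give.

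The figure in 2.3 can also be read as a count of outcome types, so it need not be a miscount. That is fair, but the five types are still not the five tests.

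On missing data, 9.5 does set an intent-to-treat rule with complete-case and multiple-imputation sensitivity analyses. Its conservative direction suggests that missing would count as not reduced, which makes the 57% figure the least likely of the three. But the rule is written for smoking status and has to be extended by inference.

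What stands is narrow: one declared secondary outcome has no analysis plan.

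**Conclusion.** The inconsistency is real and can be confirmed by counting. Sections 2.3 and 6.2.1 declare reduction of more than 50% as a secondary outcome; 9.2, 9.7 and 9.8.1 leave it out. It has no named test, no place in the corrected family and no mapping from missing to reduction status.

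The consequence is modest. The primary test at 0.01 and the five named tests at 0.002 stand as written. The bound of 0.014 applies only if someone extends 0.002 to reduction at both times, which no section proposes, and real inflation would then be slight under the assumptions above. The 43 to 57% spread shows that the missing-data rule matters for this outcome, but it depends on an assumed 50% rate and on another trial's response rate.

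The count in 2.3 and the 18% in 9.2.2 are separate matters. The 18% is a wrong stated figure: at its own inputs it has power of about 0.62, not 0.80.

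**What to change.** Before outcome data are analysed:

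1. Keep the five abstinence outcomes at 0.002 and name them as the corrected family in both 2.3 and 9.7.
2. State in 2.3 and 9.7 that reduction of more than 50% at 3 and 6 months is outside that family and reported descriptively, as a secondary or exploratory outcome. Give the scoring rule: missing counts as not reduced. Say also whether participants abstinent for 7 days count as reduced, given the 30-day recall.
3. In 9.2.2, replace the 18% detectable difference with about 21%.

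This is wording only. Cigarettes per day is already collected at baseline, 3 and 6 months, the threshold does not change and no power is lost. What is given up is a confirmatory claim on reduction.

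If that claim is wanted, count seven comparisons at 0.01/7 = 0.00143 (or use Holm starting there), add chi-square tests of reduction at 3 and 6 months with the same scoring rule, and restate the detectable differences in 9.2. These become about 0.5 point larger. At a fixed difference the loss is about 3 points of power: for 21 points over a 20% control rate, from 0.797 to 0.767.

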## 2.4 Exploratory Objectives

*Aim 2: To assess the potential effect of known and potential moderators on treatment effectiveness between the two arms.*

Exploratory analyses will examine the moderator and mediator effects on treatment effectiveness (Aim 2).

### **Moderators/Mediators of primary interest:**

- Sociodemographics: Sex, age, marital status, race/ethnicity, education level, financial burden, health insurance, internet and smartphone access and modality
- Smoking history: Years smoked, daily smoking rate, other tobacco/nicotine use (e.g., cigars, cigarettes), current/past use of tobacco treatments, nicotine dependence
- Cancer variables: Cancer type, cancer stage, treatment, and days since diagnosis
- Site characteristics: Site, geographic location, clinic volume, baseline organizational readiness, site usual care

### **Additional moderators/mediators to be explored:**

- Medical history: ECOG Performance Status, alcohol use
- Quality of life/emotions: Emotional distress, coping, anxiety, depression
- Cancer and smoking beliefs: Stigma, quit motivation, self-efficacy to quit, importance of quitting, perceived benefits of quitting smoking, quit-smoking medication beliefs
- Physical symptoms: Cravings
- Environmental influences: Level of second-hand smoke exposure, perceived social support, perceived provider support

*Aim 3: To assess the processes of implementation and dissemination (acceptability, adoption, appropriateness, treatment fidelity, cost effectiveness, penetration/reach, and sustainability) of our intervention at community oncology sites*

Guided by Proctor and colleagues' (2011) recommendations for measurement of implementation outcomes, we will explore the following to gain an initial understanding of the implementation process (Aim 3).

### **Implementation Outcomes**

- Acceptability: Patient satisfaction with content/delivery of their randomly assigned tobacco treatment
- Adoption: Site program uptake, changes in organizational readiness to deliver tobacco treatment

- Appropriateness: Perceived fit and relevance of the VIT and EUC interventions from the perspective of representative site staff
- Tobacco Treatment fidelity: Delivery of all components of the Smokefree 2.0 Study Treatment Interventions (EUC and VIT).
- Cost: Incremental cost per quit of the VIT intervention relative to the EUC control over the 6-month follow-up period
- Feasibility: Ease of delivery and suitability for routine care of the VIT and EUC interventions
- Penetration/Reach: Patient participation rate at each site, reasons for study ineligibility and refusal, comparison of sociodemographic and cancer variable characteristics of enrollees and refusers of the study
- Sustainability: Resources needed and preference for a site-based centralized tobacco treatment program

Rev. Add4

Using existing staff data collection survey and interview tools as well as synthesis of notes from minutes of monthly meetings with CCDR Leads and study investigators, we will enhance our understanding of the implementation process (Aim 3) by: 1) examining organizational characteristics that influence adoption of tobacco treatment interventions; and 2) identifying and developing strategies to address barriers for implementation of tobacco use assessment and treatment in the trial. This exploratory research will add to the limited knowledge about contextual factors influencing the engagement of community oncology sites in the adoption of tobacco use assessment and treatment; and inform how best to engage community oncology practices in the integration of smoking cessation in cancer care.

### 3. Participant Selection

#### 3.1 Selection of NCORP Site Staff Participants

In order to achieve Aim 3, we will enroll a subset of staff (n=approximately 110) from a minimum of 11 participating NCORP sites. We are seeking to elicit implementation process perspectives from key stakeholders (clinicians and research administration staff) who would most likely be instrumental in making tobacco use assessment and treatment routine part of cancer care. Guided by his/her knowledge of key stakeholders' roles and responsibilities, the Cancer Care Delivery Research (CCDR) Leader and site PI from each participating site will be responsible for identifying approximately 10 multidisciplinary staff members to complete brief (approximately 15 minute) surveys and participate in focus group interviews (approximately 45-60 minutes). The focus group interview will be conducted approximately 24-36 months after site activation, upon the completion of 36-month follow-up surveys by the site. Although specific site staff participant composition will vary somewhat by site, we envision participation of the CCDR Leader, the Site PI, 2-3 oncology nurses, 2-3 additional medical oncologists and 2-3 additional staff members.

In terms of eligibility criteria, eligible NCORP site staff participants will be English-speaking, employed at the NCORP site for at least three months, and able to provide informed consent to participate in this study (see Informed Consent for NCORP Staff). The CCDR Lead and Site PI will be responsible for consenting each other and the other staff participants. The CCDR Lead will update the REDCap Roster survey with the dates of consent for each participant. The consent date entered into the MSK REDCap Roster survey will be used as the source documentation by MSK staff to send out the baseline survey to those consented participants. Given the minimal risk, minimal burden and broad relevance of this research to CCDR priorities for enhancing high quality cancer care, we do not anticipate any difficulty recruiting staff participants. In the event that there is staff turnover, the CCDR Leader will be responsible for identifying one or more replacement staff participants who will provide 12 and 36-month follow-up surveys and participate in the focus group interview. Given our assumption that the selected staff represent key site stakeholders and that the quantitative (baseline, 12 and 36-month follow-up surveys) and qualitative data (focus group interview) will be analyzed at the level of the site, some variation in pre- and post-trial participants will be allowable and will not diminish the accomplishment of Aim 3.

##### 3.1.1 Staff Eligibility Criteria

- 3.1.1.1 Must be English speaking
- 3.1.1.2 Must be employed at NCORP site for at least three months

#### 3.2 Selection of Patients

Each of the criteria in the checklist that follows must be met in order for a patient to be considered eligible for this study. Use the checklist to confirm a patient's eligibility. For each patient, this checklist must be photocopied, completed and maintained in the patient's chart.

**In calculating days of tests and measurements, the day a test or measurement is done is considered Day 0. Therefore, if a test is done on a Monday, the Monday four weeks later would be considered Day 28.**

ECOG-ACRIN Patient No. \_\_\_\_\_

Patient's Initials (L, F, M) \_\_\_\_\_

Physician Signature and Date \_\_\_\_\_

**NOTE:** NCI Policy does not allow for the issuance of waivers to any protocol specified criteria ([http://ctep.cancer.gov/protocolDevelopment/policies\\_deviations.htm](http://ctep.cancer.gov/protocolDevelopment/policies_deviations.htm)). Therefore, all eligibility criteria listed in Section 3 must be met, without exception. The registration of individuals who do not meet all criteria listed in Section 3 can result in the participant being censored from the analysis of the study, and the citation of a major protocol violation during an audit. All questions regarding clarification of eligibility criteria must be directed to the Group's Executive Officer ([[contact]](mailto:[contact])) or the Group's Regulatory Officer ([[contact]](mailto:[contact])).

**NOTE:** Institutions may use the eligibility checklist as source documentation if it has been reviewed, signed, and dated prior to registration/randomization by the treating physician.

Rev. Add2

3.2.1 Patient Eligibility Criteria Step 0 and Step 1 (Registration)

3.2.1.1 Inclusion

\_\_\_\_\_ 3.2.1.1.1 Age  $\geq$  18 years.

\_\_\_\_\_ 3.2.1.1.2 Patient presenting with any type of cancer with a date of diagnosis within the past 4 months (124 days) at the time of Step 0 Registration.

Recurrence, diagnosed within the last 4 months, of tumors in patients with past cancer diagnoses will be considered eligible. Patients with a new primary cancer, diagnosed within the last 4 months (124 days) at the time of Step 0 Registration, who have been treated previously for other types of cancer will also be considered eligible. "In situ" cancers, diagnosed within 4 months (124 days) at the time of Step 0 Registration, will also be considered eligible.

\_\_\_\_\_ 3.2.1.1.3 Patient must be a current smoker. Current smoker is defined as any cigarette smoking (even a puff) in the past 30 days prior to Step 0 Registration.

\_\_\_\_\_ 3.2.1.1.4 Patient must be fluent in both written and spoken, English or both written and spoken, Spanish.

- 3.2.1.1.5 Patient must have telephone, e-mail access, and have access to the internet with a camera-enabled device (e.g., smartphone, tablet, computer, laptop with a webcam/camera).
- NOTE:** The restriction to those with web and e-mail access is based on the primary intention of the study; to assess the implementation of the virtual intervention in the NCORP network.
- 3.2.1.2 Exclusion (Subject must not meet any of the criteria listed here)
- 3.2.1.2.1 Patient has an ECOG performance status of 3 or above, or is deemed medically unable to participate by study investigators or oncology clinician (i.e., referral to hospice).
- 3.2.1.2.2 Patient has no intention to receive their cancer care or monitoring at an NCORP community cancer site.
- 3.2.2 Patient Eligibility Criteria Step 1 (Registration)
- 3.2.2.1 Patient must still meet all criteria outlined in Step 0
- NOTE:** The requirement to register within 4 months from cancer diagnosis is determined by the date of the Step 0 registration and not the date of the Step 1 registration.
- 3.2.3 Patient Eligibility Criteria Step 2 (Randomization)
- 3.2.3.1 Patient must have completed Baseline Survey in EASEE-PRO within 31 days of the date of Written Informed Consent (Step 1).

---

Physician Signature

Date

**OPTIONAL:** This signature line is provided for use by institutions wishing to use the eligibility checklist as source documentation.

Rev. Add2 **4. Registration and Randomization Procedures**

